9.5.3 D-dimer testing

We will estimate what the proportion of participants will be with a non-high pre-test probability (using all the possible stratification tools described above) and negative D-dimer test result and in whom imaging could potentially be withheld. We furthermore will estimate what the false negative rate will be in this proportion of participants. These proportions will be computed along with their 95% confidence intervals.

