1.2 Secondary Objectives

- To assess the utility of recalibrating the existing clinical decision rules.
- To derive a new CDR, specific to patients with a suspected recurrent VTE, and to assess whether this CDR would improve risk stratification as compared with existing CDRs.
- To assess the accuracy of D-dimer testing in patients with suspected recurrent VTE both on and off anticoagulation.
- To evaluate the accuracy of current CDRs in patients on anticoagulant therapy at the time of suspected recurrent VTE.

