6.2.2 D-dimer testing

All study patients will have a blood sample drawn at the time of suspected recurrence and frozen for central D-dimer testing. Serum samples will also be stored for future potential predictor assessment (other D-dimer assays or other biomarkers). Samples will be shipped in batches to the coordinating site and D-dimer levels will be determined in all patients using a single commercial assay (VIDAS D-dimer Exclusion II, bioMérieux Inc, Durham, NC). Please refer to the resource manual for details on processing, storage and shipping of D-dimer samples.

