9.5.2 Derivation of a new CDR

Univariate Analysis

Univariate analysis will be used to assess the association between each variable and VTE recurrence. This process will aid selection of the best variables for the multivariate analysis. The appropriate univariate technique will be chosen according to the type of data.

Multivariate Analysis

Multivariate analysis will derive one model to predict recurrent VTE. Those variables found to be strongly associated with the outcome measure ($P<0.05$), by the univariate analysis and have good inter-observer reliability ($\kappa >0.6$), will be combined using logistic regression. For continuous and ordinal variables various cut-points will be examined to determine the optimal cut-point(s). The derived CDR must be easy to use by clinicians and therefore should contain as few variables as possible. Thus, only the most informative variables will be kept in the final model. Points for the score will be attributed according to regression coefficients. The CDR will be presented in clear narrative form that does not require computation or use of statistical aids. Discrimination and calibration of the new CDR will be estimated and compared to those obtained with existed/modified CDRs using the same indices as described above.

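### Section 9.5.3 reports yield and false-negative rate for recalibrated, modified and new scores, but nothing fixes their non-high cut-off before outcomes and D-dimer are known

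*Combined protocol and SAP*

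**What the plan says.** A secondary objective (section 1.2) is to derive a new rule and "to assess whether this CDR would improve risk stratification as compared with existing CDRs". Section 9.5.3 produces two quantities. One is the share of participants described as "non-high pre-test probability (using all the possible stratification tools described above) and negative D-dimer test result and in whom imaging could potentially be withheld"; the other is the failure rate in that group ("We furthermore will estimate what the false negative rate will be in this proportion of participants"). On precision it adds only "These proportions will be computed along with their 95% confidence intervals". The tools described above it are the existing rules (9.5), the recalibrated and modified rules (9.5.1) and the new rule (9.5.2).

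Published bands appear in Appendices A and B, for the Wells DVT, Wells PE and revised Geneva rules only. For the new rule, section 9.5.2 says "Points for the score will be attributed according to regression coefficients" and sets no bands on the total. The cut-points it mentions are for individual predictors. Section 9.5.1 does not say whether an existing band survives a change in points or an added item. Sections 9.5 to 9.5.3 contain no target risk, no rule for choosing a cut-off, no lock and no bootstrap, cross-validation or held-out sample.

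D-dimer is measured centrally ("Samples will be shipped in batches to the coordinating site", section 6.2.2). It is also listed among the candidate predictors (section 2.2.2, Appendix D), and local results of all diagnostic tests are recorded (section 6.2.1).

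**The concern.** Section 2.2 names the weakness of current practice: only 10-16% of patients can have VTE excluded by low pretest probability plus a negative D-dimer. Section 2.1 wants improved stratification to raise that yield. Section 9.5.3 is where a reader will look to see whether a new score does so safely.

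Yield and failure rate both rise as the cut-off rises, so neither means much until the cut-off is fixed. The existing rules are held to published values. The other scores get their scale from coefficients fitted to the adjudicated outcome, so a cut-off on that scale comes after the outcome data unless a rule is set beforehand. Nothing keeps D-dimer out of view at that point. A larger yield obtained by a looser cut-off is not better stratification, and a low failure rate at a cut-off picked for its low observed failure rate is optimistic.

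**Working it through.** **1. The plan's own figure.** Section 9.2: 100/0.29 = 344.8, so 345 for DVT; 100/0.25 = 400 for PE; total 745, as stated. The plan gives no cut-off, yield or failure figure for a new score, so what follows is illustration.

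**2. Inputs.** From section 9.2: confirmation rate p = 25% (PE, N=400) and 29% (DVT, N=345). From section 2.2: D-dimer negative in 16% (49/308) of suspected PE with prior VTE and in 45% of 300 with suspected recurrent DVT; m = 16% and 44% are used here. Assumed: D-dimer sensitivity (Se) 95%, score c-statistic 0.72, normally distributed score, D-dimer independent of the score given disease status. Implied specificity Sp = [m − p(1−Se)]/(1−p):

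- PE: (0.16 − 0.0125)/0.75 = 0.197
- DVT: (0.44 − 0.0145)/0.71 = 0.599

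Yield cannot exceed m. If everyone were called non-high, failure would be 0.0125/0.16 = 7.8% (PE) and 0.0145/0.44 = 3.3% (DVT). Expected D-dimer-negative cases number only 400×0.0125 = 5 and 345×0.0145 = 5, so one or two patients decide the observed rate.

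**3. Moving the cut-off of one unchanged score.** Let q be the share called non-high and v the VTE prevalence among them; v follows from score means separated by √2·Φ⁻¹(0.72) = 0.824. Then yield = q·v·(1−Se) + q·(1−v)·Sp, and failure = q·v·(1−Se)/yield.

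| | q | v | yield | failure |
|---|---|---|---|---|
| PE | 30% | 9.9% | 0.0015 + 0.0532 = 5.5% | 2.7% |
| PE | 90% | 21.5% | 0.0097 + 0.1389 = 14.9% | 6.5% |
| DVT | 30% | 12.1% | 0.0018 + 0.1580 = 16.0% | 1.1% |
| DVT | 90% | 25.3% | 0.0114 + 0.4027 = 41.4% | 2.7% |

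Discrimination is identical in both rows of each pair.

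**4. Tuning the cut-off on observed failures.** Simulated studies under the same assumptions, averaged over those in which a qualifying cut-off existed:

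| Selection | PE apparent / true | DVT apparent / true |
|---|---|---|
| Largest yield, observed failure ≤2% | 0.7% / 4.4% | 1.5% / 2.3% |
| Largest yield, no observed failure | 0% / 3.7% | 0% / 1.6% |

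On the cut-off grid used, a zero-failure cut-off existed in about 55% of simulated studies.

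**5. Sensitivity.** With c-statistic 0.70, specificity 25% (PE) and 60% (DVT), hence negative shares of 20% and 44%, and a cut-off allowed anywhere: at ≤2%, 0.7% against 3.2% (PE) and 1.4% against 2.3% (DVT); at zero failures, 0% against 2.6% and 1.3%. With c-statistic 0.75, the ≤2% results are 0.9% against 3.0% and 1.5% against 2.2%. The direction is constant and the size is not.

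**6. Does a pre-set rule remove it?** Under the assumptions of step 2, setting the cut-off by matching VTE prevalence to a comparator rule, blind to D-dimer, gave apparent and true failure rates of 5.6% and 5.6% (PE) and 2.3% and 2.4% (DVT). The level depends on the comparator assumed; the agreement is the point.

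None of these figures includes the further optimism from selecting predictors, cut-points and weights in the same data.

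**The case against.** The plan is silent on how the cut-off is chosen. A reader might infer that it prescribes a choice after the data are seen, or that it aims for zero failures; it says neither, and it names no failure target. For the new score, timing after the outcome follows from how the points are made. Tuning on failures is a possibility the plan leaves open.

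A reader might also infer a formal contest on yield. Section 9.5.3 only says it will estimate. The comparison stated in words, in 9.5.2, is of discrimination and calibration, and neither the c-statistic nor the Integrated Discrimination Improvement needs a band on the total score. Net Reclassification Improvement does if it is computed on categories. Even so, the same two proportions are reported for every tool under an objective of improvement, so they will be read side by side.

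Nor can yield be set at will. It is capped by the D-dimer-negative share, and for PE at a 16% share the zero-failure choice gives a mean yield of about 7%, below the 10-16% to be beaten. That choice would not create an apparent gain in PE yield.

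Finally, the intervals are wide. With 0 failures in 40, the exact upper limit is 1 − 0.025^(1/40) = 8.8%, and in simulation such limits covered the true rate about 98% of the time. So the interval ignores the selection but usually still contains the truth. The bias lies in the point estimate and in the comparison of yields. That objection limits the harm without removing it.

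**Conclusion.** The concern holds in a limited form. For recalibrated, modified and new scores, non-high is undefined and nothing prevents its being set with outcome and D-dimer in hand. If it is tuned on observed failures, the reported false-negative rate is too low: by 3.7 percentage points for PE (4.4 − 0.7) and 0.8 for DVT (2.3 − 1.5) at a ≤2% criterion, under the assumptions in step 2 of the working. These sizes depend on assumed D-dimer and score performance and on the cut-off grid. The documents do not support saying that the bias will occur, only that the plan leaves it open.

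The primary validation of existing rules at their published bands is not affected by this point. Separately, Appendix E treats recurrence as excluded when an existing rule is non-high and D-dimer is negative. That pulls the existing rules' failure rate toward zero by definition, and the illustration leaves it out.

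**What to change.** This is an inexpensive improvement to a secondary analysis. In 9.5.2 and 9.5.3:

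- For each recalibrated, modified or new score, define non-high as the highest cut-off at which VTE prevalence in the non-high group is no higher than in the non-high group of a named existing rule, in the same participants. Do this separately against each published banding in Appendices A and B (Wells DVT; Wells PE at two and at three levels; revised Geneva).
- Keep D-dimer, central or locally recorded, out of the scores evaluated in 9.5.3. Report any model containing D-dimer separately.
- Lock scores and cut-offs before any D-dimer result is merged. Batched central testing makes this practical, but locally recorded results must be withheld too. The lock does not remove D-dimer information that enters the outcome through Appendix E.
- Then report the paired difference in yield, and the failure rates, with 95% confidence intervals. The cut-off still uses outcomes from the derivation sample, so correct for optimism by bootstrapping the whole derivation, including the cut-off step.

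The cost is SAP wording, a data-release step and some extra analysis, with no added participants or visits. The cut-off will not be tuned for maximum yield, and D-dimer cannot enter these scores.

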Post-hoc analyses of diagnostic studies have been reassuring in terms of the safety of ruling out VTE on the basis of a non-high pretest probability using the Wells or Geneva rule in combination with a negative D-dimer in patients with a previous history of VTE.^{4,9} However, the proportion of patients in whom the diagnosis could be ruled out non-invasively was very low: approximately 10%, as compared with 30% among all-comers with suspected VTE.¹⁰

Moreover, residual thrombosis is often present after a VTE event (up to 50% of patients at one year). Therefore, it is more likely to misdiagnose a recurrent VTE in saying it is present, while it's absent. As a result of over diagnosis, these patients have a long period of exposure to anticoagulants and the associated risk of major bleeding.

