In patients with a suspected VTE event, D-dimer testing, in combination with a CDR, can safely rule out a VTE.^{7;23} In a study in 300 patients with clinically suspected recurrent DVT by Rathbun et al., 45% of the 300 patients had a negative D-dimer test and these patients were not treated with anticoagulants on the basis of this test alone.²⁰ One patient who had recurrent DVT excluded by a negative D-dimer test had confirmed VTE during 3 months follow-up (0.75% (95% CI, 0.02-4.09%). The Wells score in combination with a D-dimer test has been used to manage patients with clinically suspected acute recurrent DVT in a study by Anderson et al.¹⁹ In this study, 16 of 105 patients (15%) had an unlikely clinical probability and a normal D-dimer test; during three months follow-up none of these patients had a recurrent DVT. This study suggests that an unlikely clinical probability in combination with a normal D-dimer test result could potentially be used to exclude a DVT, but this strategy should be evaluated in a larger cohort of patients. The proportion of confirmed recurrent DVT was 22%. In a third study, among 308 patients with suspected acute PE with a VTE in the past, the D-dimer test was negative in 49 patients (16%), and none of them had a recurrent VTE during the 3-month follow-up: failure rate 0% (95% CI, 0.0-7.9%). The proportion of confirmed recurrent PE was 40%.⁴

In conclusion, D-dimer testing may play a role in excluding a recurrent VTE; however the presently available studies show broad confidence intervals for the 3 month recurrent VTE failure rates after a negative test result. Most importantly, the combination of current CDRs and D-dimer testing shows a low proportion (10-16%) of patients who could have VTE excluded by a low pretest probability and a negative D-dimer test result.

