9.5 Primary Outcome Analysis

The primary analysis is the validation of existing CDRs. The Wells DVT score will be computed in all participants with suspected DVT, and both the Wells' PE score and revised Geneva score will be computed in participants with suspected PE. Calibration will be assessed by comparing predicted and observed rates of confirmed VTE (Hosmer-Lemeshow 'goodness-of-fit test'), and discrimination will be assessed using the area under the receiver operating characteristics curve (c-statistic). Further, the proportion of participants with the combination of a non-high clinical probability and negative D-dimer test, and the false-negative rate of this combination (ie the proportion of participants with confirmed recurrent VTE among those with a non-high clinical probability and negative D-dimer) will be estimated along with their 95% confidence intervals.

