9.6 Secondary Outcome Analysis

9.5.1 Recalibration / minor adjustment to existing rules

Recalibration

For each existing CDR, a multivariate regression analysis including all predictors from the CDR will be conducted. The regression coefficients obtained from this model in our sample will be examined to evaluate whether changes in the points given to each predictor in the rule need to be modified in patients with a suspected recurrent VTE.

Minor adjustments

For each existing CDR, a multivariate regression analysis including all predictors from the CDR will be performed. Candidate predictors will also be included in the analysis, but keeping in the model predictors from the CDR. Should one or two candidate predictors significantly improve risk stratification, a modified score could be proposed for patients with suspected recurrent VTE. Potential improvements in classification will be assessed using the Net Reclassification Improvement and the Integrated Discrimination Improvement indices.

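### The share of patients who could skip imaging is reported rule by rule with separate intervals; no between-rule difference is planned, although the rules are scored on the same participants within suspected DVT and within suspected PE

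*Combined protocol and SAP*

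**What the plan says.** The comparative aim is in section 1.2: derive a new rule and "to assess whether this CDR would improve risk stratification as compared with existing CDRs". The background presents low yield as the problem. Section 2.1 puts the proportion ruled out without imaging in patients with previous VTE at "approximately 10%, as compared with 30% among all-comers with suspected VTE". Section 2.2 says that current rules plus D-dimer testing "shows a low proportion (10-16%) of patients who could have VTE excluded by a low pretest probability and a negative D-dimer test result". Section 2.1 also names a higher yield of rule plus D-dimer, and so less imaging, as the clinical value of better stratification.

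Section 9.5 estimates the rule-out proportion and its false-negative rate for the existing rules, each with a 95% CI. Section 9.5.3 repeats this "using all the possible stratification tools described above", and adds: "These proportions will be computed along with their 95% confidence intervals".

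The plan does compare rules on other measures. For modified rules, section 9.5.1 states: "Potential improvements in classification will be assessed using the Net Reclassification Improvement and the Integrated Discrimination Improvement indices". For the new rule, section 9.5.2 states: "Discrimination and calibration of the new CDR will be estimated and compared to those obtained with existed/modified CDRs".

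On who is scored, section 9.5 computes the Wells DVT score in suspected DVT, while "both the Wells' PE score and revised Geneva score will be computed in participants with suspected PE".

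**The concern.** The benefit claimed for a new or modified rule is that more patients could avoid imaging. That quantity gets one estimate and one interval per rule, with no estimate of the gain and no interval for it. A reader who wants the gain must set two intervals side by side, and those intervals ignore that both proportions come from the same people.

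The overlap between rules is likely to be large. Every rule's rule-out group lies inside the same D-dimer-negative group, measured with one central assay (section 6.2.2), so two rules can disagree only so far. Separate intervals discard that information. At stake is a gain of a few percentage points, which separate intervals would leave unclear and a paired difference would usually show.

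**Working it through.** **Plan's own figure.** 100/0.29 = 344.8, so 345 suspected DVT; 100/0.25 = 400 suspected PE; 345 + 400 = 745. This reproduces section 9.2.

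**Inputs.** From the documents: n = 400 (PE) and n = 345 (DVT), section 9.2; current yield 10-16%, section 2.2. Assumed: a yield of about 15% with the new rule, and the discordance between rules. The documents give neither, so discordance is shown as a range.

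**Formulas.** Let b be the number ruled out by the new rule only and c the number ruled out by the existing rule only.
- Separate intervals: exact (Clopper-Pearson).
- Paired difference: d = (b - c)/n, SE = sqrt(b + c - (b - c)²/n)/n, CI = d ± 1.96 SE; P from the exact McNemar test.
- Unpaired SE: sqrt(p1(1 - p1)/n + p2(1 - p2)/n).

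**Suspected PE, 40/400 versus 60/400.**
- Separate intervals: 10.0% (7.2-13.4) and 15.0% (11.6-18.9). They overlap.
- Unpaired: SE = sqrt(0.10 × 0.90/400 + 0.15 × 0.85/400) = 0.0233, so 5.0 points (0.4 to 9.6).
- Paired, by the share of the 40 current exclusions that the new rule loses:

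| Lost | b | c | SE (points) | 95% CI (points) | McNemar P |
|---|---|---|---|---|---|
| none | 20 | 0 | 1.1 | 2.9 to 7.1 | < 0.0001 |
| 15% | 26 | 6 | 1.4 | 2.3 to 7.7 | 0.0005 |
| 25% | 30 | 10 | 1.6 | 1.9 to 8.1 | 0.002 |
| 50% | 40 | 20 | 1.9 | 1.2 to 8.8 | 0.013 |

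For the last row: sqrt(60 - 20²/400)/400 = sqrt(59)/400 = 0.0192. Relative to the unpaired SE of 2.3, that is 18% smaller; with 15% lost it is 40% smaller.

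**Suspected DVT, 35/345 versus 52/345 (b = 23, c = 6).** d = 17/345 = 4.9 points; SE = sqrt(29 - 17²/345)/345 = 0.0154; CI 1.9 to 7.9; P = 0.002. Treated as unpaired, SE = 0.0252 and the CI just reaches zero (-0.01 to 9.9).

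**Where it matters.** The table gives the gain, in points, from a 10% / 16% base. Separate intervals here are Wilson; the paired range runs from 0% to 50% of current exclusions lost.

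| n | Gain at which separate intervals stop overlapping | Smallest gain with McNemar P < 0.05 |
|---|---|---|
| 345 | 7.2 / 8.7 | 1.7-4.3 / 1.7-5.2 |
| 400 | 6.8 / 8.0 | 1.5-4.0 / 1.5-4.8 |

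Pairing does not rescue every small gain. At n = 400 from a 16% base, a 4-point gain with half of current exclusions lost (b = 48, c = 32) has a CI of -0.4 to 8.4. Conversely, a rise from 10% to 30% at n = 400 is plain from separate intervals (7.4-13.3% and 25.7-34.7%).

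**Precision of the safety figure.** If 26 participants are newly ruled out and none has a recurrence, the exact upper 95% limit is 1 - 0.025^(1/26) = 13.2%.

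**The case against.** The strongest reply is that the comparative objective speaks of risk stratification, and the plan already compares rules on it. NRI and IDI use each participant's classification under both models, so they exploit the pairing, and section 9.5.2 compares discrimination and calibration. Section 9.5.3 is worded as estimation under a D-dimer heading. This stands, and it limits the point to one further measure that lacks a contrast. It does not remove the point, because none of those indices gives the share in whom imaging could be withheld after D-dimer.

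A reader might infer that the plan will judge rules by overlapping intervals and call a real gain unproven. No section says so; the plan is silent on how the proportions will be compared. In the PE illustration even an unpaired difference excludes zero (0.4 to 9.6), so the gap is first that no difference is planned, and only then that pairing is unused.

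A reader might also infer that all rules are scored on all participants. They are not: Wells DVT and the two PE rules are applied to different groups, so pairing holds only within a suspicion type. Nor does any objective ask which PE rule excludes more patients, so a Wells PE versus Geneva contrast can only be descriptive.

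Finally, a paired interval is not free of risk. Section 9.5.2 selects variables, searches cut-points and assigns points in this same cohort. A naive paired interval would treat the new rule as fixed in advance and overstate its gain. That objection is sound, and the fix has to meet it.

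**Conclusion.** The point holds as a modest gain in precision on data that will be collected anyway. For rule-out yield, the benefit on which the protocol rests its case, the plan gives no between-rule difference. Within suspected DVT and within suspected PE, a paired difference would be more precise: in the 10% versus 15% illustration its SE is at most 1.9 points against 2.3 unpaired, and its CI excludes zero across the whole assumed discordance range.

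The size depends on the assumed discordance and the assumed gain. It matters mainly for gains of roughly 3 to 6 points at n = 345-400, and some of those remain inconclusive when many current exclusions are lost. The illustrations also treat the new rule as fixed, so they show sampling precision before any optimism correction. The documents do not support a claim that the planned analysis would miss a clinically large gain, or that the comparative objective has no analysis.

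**What to change.** Add to section 9.5.3, separately for suspected DVT and suspected PE:

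1. The paired difference in rule-out proportion with its 95% CI, for each new or modified rule minus the existing rule; and, descriptively, Wells PE minus revised Geneva.
2. For any rule derived or modified in this cohort, correct the difference and its CI for optimism by bootstrapping the whole derivation, including variable selection, cut-points and the choice of the non-high threshold.
3. Beside it, the failure rate with an exact CI among participants newly moved into the rule-out group, with a note that it will be imprecise. A McNemar test should not be used to compare the rules' overall false-negative rates, because each rule has a different denominator.
4. In sections 9.5.1 and 9.5.2, state that c-statistics are compared with a method for paired data.

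The cost is a short paragraph of text and modest extra programming, with no new data or participants. The downside is that an optimism-corrected gain will look smaller than the apparent one.
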